### **7.3.3 Medical History**

General medical history will be listed by subject.

### **7.3.4 Prior Therapy**

The following will be summarized by cohort for the all treated population.

- Prior neo-adjuvant therapy (yes/no)
- Prior adjuvant therapy (yes/no)
- Time from completion of prior adjuvant therapy to assignment (subjects who received prior adjuvant therapy), (< 6 months and ≥ 6 months)
- Prior surgery related to cancer (yes/no)
- Prior radiotherapy (yes/no)
- Number of prior therapies received (2, 3, ≥4)
- Best response to most recent prior regimen (CR/PR vs SD vs PD)
- For SCLC cohort: Time from first line treatment to start of second line treatment (≤ 90 days and > 90 days)
- Prior platinum experience (cisplatin only, carboplatin only, both or other) by setting
- Characteristics of the most recent prior platinum regimen associated with recurrence/progression: Best response, reason off-treatment and time from last dose to recurrence/progression
- Time from completion of most recent prior regimen to study treatment (< 3, 3 - < 6, ≥ 6 months)

Agents and medication will be reported using the generic name. A listing by subject will also be provided.

### **7.3.5 Baseline Examinations**

Subjects with abnormal baseline physical examination will be tabulated by examination criteria, treatment group, and tumor type for all treated subjects.

## **7.4 Extent of Exposure**

Analyses in this section will be performed in all treated subjects.

For the analyses of crossover subjects during original assigned treatments, the exposure will be truncated at the first crossover dose date. All others will follow regular counting rules. For the analysis of crossover subjects during crossover period, the exposure will be started at the first crossover dose date.

#### **7.4.1 Administration of Study Therapy**

The following parameters will be summarized (descriptive statistics) by cohort:

- Relative dose intensity (%) using the following categories: <50%; 50 - <70%; 70 - <90%; 90 - <110%, ≥110%.
- Number of doses of nivolumab, ipilimumab (summary statistics)
- Cumulative dose of nivolumab, ipilimumab

Duration of treatment will be presented by cohort using a Kaplan-Meier curve whereby the last dose date will be the event date for those subjects who are off study therapy. Median duration of treatment and associated 95% CI will be provided. Subjects who are still on study therapy will be censored on their last dose date.

A by-subject listing of extent of exposure (weight, number of doses, date of first and last dose, cumulative dose, relative dose intensity, duration of treatment, and reason for discontinuation) will be provided.

**Table 7.4.1-1: Study Therapy Parameter Definitions**

	Nivolumab in Arm N and Arm N-I Dose Level 2c	Nivolumab in Arm N-I Dose Levels 1, 2 and 2b	Ipilimumab in Arm N-I Dose Levels 1, 2, 2b, and 2c
Dosing Schedule per Protocol	3 mg/kg every 2 weeks	1 or 3 mg/kg every 3 weeks for 4 doses followed by 3 mg/kg every 2 weeks OR Maximum tolerable dose identified in escalation phase. MTD may differ by tumor type	1 or 3 mg/kg 3 weeks for 4 doses or 1mg/kg 6 weeks (2c)
Dose	Dose (mg/kg) is defined as the minimum of [vial strength (mg/mL) *total volume infused (mL)] /most recent weight (kg) and nominal dose (mg/kg) * total volume infused (mL) /total volume prepared (mL)	Dose (mg/kg) is defined as the minimum of [vial strength (mg/mL) *total volume infused (mL)] /most recent weight (kg) and nominal dose (mg/kg) * total volume infused (mL) /total volume prepared (mL)	Dose (mg/kg) is defined as the minimum of [vial strength (mg/mL) *total volume infused (mL)] /most recent weight (kg) and nominal dose (mg/kg) * total volume infused (mL) /total volume prepared (mL)
Cumulative Dose	Cum Dose (mg/kg) is the sum of the doses administered to a subject.	Cum Dose (mg/kg) is the sum of the doses administered to a subject.	Cum Dose (mg/kg) is the sum of the doses administered to a subject.
Dose Intensity (%)	7x Cum dose/(Last dose date - Start dose date + 14)	For Combo phase (the first two cycles): 7x Cum dose in Combo phase / (Last dose date in Combo phase - Start dose date + 21) For Mono phase (cycle 3 and beyond): 7x Cum dose in Mono phase / (Last dose date - Start dose date in Mono phase + 14)	7 x Cum dose/(Last dose date - Start dose date + 21) For 2c: 7 x Cum dose/(Last dose date - Start dose date + 42)
Relative Dose Intensity (%)	Cum dose /[(Last dose date - Start dose date + 14) x 3/14] x 100	Cum dose/[(3 or 1) x (Last dose date - Start dose date + 21)/21] x 100, if the last dose is in Combo phase Cum dose/[(3 or 1) x 4 + 3 x (Last dose date - 84 + 14)/14] x 100, if the last dose is in Mono phase	Cum dose/[(3 or 1) x (Last dose date - Start dose date + 21)/21] x 100 For 2c: Cum dose/[(1) x (Last dose date - Start dose date + 42)/42] x 100
Duration of Treatment	Last dose date - Start dose date +1	Last dose date - Start dose date +1	Last dose date - Start dose date +1

Volume infused, volume prepared, and weight are collected on the CRF. Nominal nivolumab dose collected in IVRS.  $i = 1, 2, \dots, N$ , where  $N =$  number of infusions. Cycle Duration  $(N) = 3$  weeks for nominal 1 or 3 mg/kg nivolumab doses and 2 weeks for nominal 3 mg/kg. Intended dose per week is .33 or 1 mg/kg

for nominal 1 or 3 mg/kg nivolumab doses and 1.5 mg/kg for nominal 3 mg/kg nivolumab doses. If different from the above dosing, the MTD will be used for ARM N-I and may vary by tumor type.

## **7.4.2 Modifications of Study Therapy**

### **7.4.2.1 Dose delays**

Each nivolumab and ipilimumab infusion may be delayed. A dose will be considered as actually delayed if the delay is exceeding 3 days (i.e., greater than or equal to 4 days from scheduled dosing date) for both nivolumab and ipilimumab. All studies drugs must be delayed until treatment can resume. Reason for dose delay will be retrieved from CRF dosing pages.

The following parameters will be summarized by cohort:

- Number of dose delays per subject, length of delay (4 - <8 days, 8 - <15 days, 15- <42 days,  $\geq$  42 days), and reason for delay

### **7.4.2.2 Infusion Interruptions and Rate Changes**

Each nivolumab or ipilimumab infusion can be interrupted and/or the IV infusion rate can be reduced. This information will be retrieved from CRF dosing pages.

The following parameters will be summarized by cohort:

- Number of subjects with at least one dose infusion interruption, the reason for interruption, and the number of infusion interruptions per subject.
- Number of subjects with at least one IV infusion rate reduction and the reason for reduction.

### **7.4.2.3 Dose Escalations**

Dose escalations are not permitted for either nivolumab or ipilimumab.

### **7.4.2.4 Dose Reductions**

Dose reductions are not permitted for either nivolumab or ipilimumab.

### **7.4.2.5 Dose Omissions**

Dose omissions are not permitted for either nivolumab or ipilimumab.

## **7.4.3 Administration and Modifications of Study Therapy Post Crossover**

The following parameters will be summarized (descriptive statistics) based on exposure data collected in treated crossover subjects on or after the first date of active ipilimumab therapy.

- Number of ipilimumab and nivolumab doses received post crossover.
- Cumulative ipilimumab and nivolumab dose post crossover.
- Relative ipilimumab and nivolumab dose intensity (%) post crossover using the following categories: < 50%; 50 - < 70%; 70 - < 90%; 90 - < 110%;  $\geq$  110%.
- Number of ipilimumab and nivolumab dose delays post crossover per subject, length of delay, and reason for delay.
- Number of subjects with at least one dose infusion interruption post crossover, the reason for interruption, and the number of infusion interruptions per subject.
- Number of subjects with at least one IV infusion rate reduction post crossover and the reason for reduction.

## **7.5 Efficacy**

Efficacy analyses will be performed on all treated subjects, except where otherwise indicated.

### **7.5.1 Objective Response Rate**

#### **7.5.1.1 Primary Analysis**

ORR will be summarized for each cohort by a binomial response rate and corresponding two-sided 95% exact CI using the method proposed by Atkinson and Brown for cohorts using two-stage design and Clopper and Pearson method for cohorts using one stage design.

DOR will be summarized for subjects who achieve confirmed PR or CR using the Kaplan-Meier product-limit method. Median values of DOR, along with two-sided 95% CI using the log-log transformation will also be calculated by cohort. In addition, the percentage of responders still in response at different time points (3, 6, and 12 months) will be presented based on the KM plot.

For SCLC expansion cohorts, similar methods will be used to summarize ORR and DOR for each stratification factor.

The magnitude of reduction in tumor burden will be summarized descriptively.

For the analyses of crossover subjects during original assigned treatments, ORR data will be truncated prior to the first crossover dose date. For the analysis of crossover subjects during crossover period, ORR will also be summarized. Baseline will be re-established. BOR, PR, and CR will be re-derived starting on the date of crossover.

In addition, percent change from baseline based on the target lesions will be plotted overtime for each subject grouped by treatment arm (spider plot). For crossover subjects, data will be truncated prior to the first date of crossover.

Time on therapy and time to response will also be plotted for each subject with symbols indicating time of radiographic progression, LKDA, first response, last dose, last dose when subject off treatment, crossover, and death (swimmer plot). For crossover subjects, no data will be truncated.

- A plot of individual time course of tumor burden change per investigator assessment but limited to subjects who were treated beyond progression.

Among subjects treated beyond progression, non-conventional benefitters will be identified and will be defined as subjects who had not experienced a BOR of PR/CR prior to initial RECIST-defined progression, and met at least one of the following:

- Criterion 1: Appearance of a new lesion followed by decrease from baseline of at least 10% in the sum of the target lesions.
- Criterion 2: Initial increase from nadir  $\geq 20\%$  in the sum of the target lesions followed by reduction from baseline of at least 30%.
- Criterion 3: Initial increase from nadir  $\geq 20\%$  in the sum of the target lesions or appearance of new lesion followed by at least 2 tumor assessments showing no further progression defined as a 10% additional increase in sum of target lesions and new lesions.

## **7.5.2 Progression Free Survival**

### **7.5.2.1 Primary Analysis**

The PFS curves for each cohort will be estimated using the KM product-limit method. Two-sided, 95% confidence intervals for median PFS will be computed using the log-log transformation.

PFS rates at 3, 6, and 12 months will be estimated using KM estimates on the PFS curve for each cohort. Minimum follow-up must be longer than the timepoint to generate the rate. The associated two-sided 95% CI will also be calculated.

The source of progression (death vs. progression) will be summarized.

The status of subjects who are censored in the PFS KM analysis will be tabulated for each cohort using the following categories:

- On-study (on-treatment, in follow-up)
- Off-study (lost to follow-up, withdrawn consent, never treated)
- Received subsequent anti-cancer therapy

### **7.5.2.2 Sensitivity Analysis**

Sensitivity analyses of PFS will also be performed using the following modification:

- PFS accounting for assessment on/after subsequent therapy. PFS will be defined similarly to the primary analysis except that events (progression or death) and tumor assessments that occurred on or after subsequent anti-cancer therapy will be taken into account.

## **7.5.3 Overall Survival**

OS curves for each cohort will be estimated using the Kaplan-Meier (KM) product limit method. Median OS and the corresponding two-sided 95% confidence intervals using the log-log transformation will be computed. Survival rates at 3, 6, 12, 18, 24, 36, 48, and 60 months will be estimated using KM estimates on the OS curve for each cohort. Minimum follow-up must be longer than the timepoint to generate the rate. Associated two-sided 95% CIs will be calculated.

For crossover subjects, no data will be truncated.

#### **7.5.3.1 Subject Follow-up**

The extent of follow-up defined as the time between assignment date and last known date alive (for subjects who are alive) or death date (for subjects who died) will be summarized descriptively (median, min, max) for all assigned subjects.

The currentness of follow-up, defined as the time between last OS contact (i.e., last known date alive or death date) and data cut-off date, will be summarized by cohort. Subjects who died and subjects with a Last Known Date Alive on or after LPLV will have a value of '0' for currentness of follow-up. The currentness of follow-up will be categorized into the following categories: 0 days, 1-30 days, 31-60 days, 61-90 days, 91-120 days, 120-150 days, 151 or more days.

#### **7.5.3.2 Subsequent Therapy**

Subsequent therapy and response to subsequent therapy will be summarized and listed.

- Subsequent Therapy
  - Chemotherapy by drug name
  - Hormonal or biologic therapy by drug name
  - Immunotherapy (anti-PD1 agents, anti-PDL1 agents, anti-CTLA4 agents, and others) by drug name
  - BRAF inhibitor by drug name
  - MEK/NRAS inhibitor by drug name
  - Other investigational agent by drug name
  - Surgery
  - Radiotherapy
  - Any combination of the above

A by-subject listing of follow-up therapy will be produced for subjects who had any subsequent therapy.

#### **7.5.4 Interim Analyses**

Data will be reviewed during the Dose Escalation Safety Evaluation Phase to determine the maximum tolerated dose level for arm N-I and to make decisions about Stage 2 for each cohort. The decision to proceed from Stage 1 to Stage 2 will be conducted for TNBC, GC, PC, and SCLC treatment arms with two-stage design independently.

Interim analyses may be conducted after Stage 1, by cohort. These interim analyses may be triggered if a “super” response (i.e. 8 or more responders out of 18 subjects) is observed or if it is necessary in order to make decisions regarding further development and supporting external disclosure such as medical conference. Summaries and listings of efficacy and safety will be provided. This interim analysis will not impact the study duration and the trial will continue as planned.

For BC and OC cohorts, one-stage design is used. The interim analysis will be conducted by cohort to support internal decision making and publication disclosure.

For new SCLC expansion cohorts, no interim analysis will be performed.

## **7.6 Safety**

For all safety related analyses, refer to the Core Safety SAP. Safety will be summarized for: all treated subjects, by cohort; all dose escalation subjects, by tumor type; and all crossover subjects, by tumor type.

For the analyses of crossover subjects during original assigned treatments, all the AE will be truncated at the first crossover dose date. All others will follow regular counting rules. For the analysis of crossover subjects during crossover period, all the AE will be counted at the first crossover dose date.

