## **2 STUDY DESCRIPTION**

### **2.1 Study Design**

This is a Phase 1/2, open-label study of nivolumab monotherapy (Arm N), or nivolumab combined with ipilimumab (Arm N-I) in adult ( $\geq 18$  years) subjects with advanced or metastatic cancer of the following types:

- 1) Triple Negative Breast Cancer (TNBC)
- 2) Gastric or Gastro-Esophageal Junction Carcinoma (GC)
- 3) Pancreatic Cancer (PC)
- 4) Small Cell Lung Cancer (SCLC)
- 5) Bladder Cancer (BC).
- 6) Ovarian Cancer (OC)

The assignment to treatment arm and evaluation of safety and activity will be performed independently for each tumor type. For each tumor type, subjects will be assigned to one of these treatment arms:

**Arm N:** Nivolumab monotherapy (3 mg/kg) Q2W

**Arm N-I Dose Level 1:** Nivolumab (1 mg/kg) + Ipilimumab (1 mg/kg) Q3W for 4 doses, then Nivolumab (3 mg/kg) Q2W

**Arm N-I Dose Level 2:** Nivolumab (1 mg/kg) + Ipilimumab (3 mg/kg) Q3W for 4 doses, then Nivolumab (3 mg/kg) Q2W

**Arm N-I Dose Level 2b:** Nivolumab (3 mg/kg) + Ipilimumab (1 mg/kg) Q3W for 4 doses, then Nivolumab (3 mg/kg) Q2W

**Arm N-I Dose Level 2c:** Nivolumab (3 mg/kg) Q2W + Ipilimumab (1 mg/kg) Q6W

Additional cancer types may also be added in the future. The addition of any new cancer types will not affect the statistical analysis plan. All analyses related to the additional cancer types will be performed exactly as described in this SAP.

**Dose-Escalation Safety Evaluation Phase for Combination Arm:** Although the regimen currently used in the phase 3 melanoma study, nivolumab 1 mg/kg IV + ipilimumab 3 mg/kg, was expected to also be tolerable in the tumors studied here, an initial dose-escalating safety evaluation for the combination arms was conducted for each subject with GC, PC, TNBC, or SCLC. The BC cohort was added to this protocol following the completion of the safety evaluations in GC, PC, TNBC, and SCLC at dose level 1 (nivolumab 1 mg/kg, ipilimumab 1 mg/kg) which did not reveal safety concerns. Thereby the starting dose level for the BC cohort was dose level 2 (nivolumab 1 mg/kg, ipilimumab 3 mg/kg). Six BC patients were initially randomized to Dose Level 2, after which enrollment to Dose Level 2b (nivolumab 3 mg/kg, ipilimumab 1 mg/kg) began.

Enrollment to Stage 1 for Arm N will occur in parallel to the safety evaluation for Arm N-I.

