For Stage 2, additional subjects will be assigned into Arm N, and Arm N-I up to a total of 100 subjects (including those assigned in Stage 1) in each treatment arm of the given tumor type. For tumor types where nivolumab monotherapy or nivolumab 1 mg/kg plus ipilimumab 3 mg/kg proceeded to Stage 2, assessment of Dose Level 2b in Stage 2 (nivolumab 3 mg/kg + ipilimumab 1 mg/kg, n= up to 60 subjects) will be initiated for that tumor type. For SCLC, an additional 150 2L and 3L subjects (50% each) will be added in the nivolumab monotherapy arm, 100 2L and 3L subjects (50% each) will be added to N-I dose level 2.

**Crossover for subjects in Arm N:** Subjects in Arm N may crossover to Arm N-I if all of the following criteria are met:

- The Safety Evaluation Phase for the N-I regimen has been completed and at least 6 subjects have been exposed to the dose level used for Stage 1 of the N-I regimen. In case Dose Level 2b has been activated and completed the safety assessment, subjects for cross over will be assigned to Dose Level 2b.
- Subject has confirmed radiologic disease progression (investigator-assessed RECIST 1.1-defined progression confirmed at least 4 weeks after the initial tumor assessment showing progression) in the absence of clinical deterioration. For subjects with clear evidence of new or progressing brain metastases a confirmation is not required. These subjects may proceed with brain radiation therapy and after having completed the radiation therapy a cross over to Arm N-I can be considered
- Subject has not experienced nivolumab related adverse events leading to permanent discontinuation.
- Subject is not continuing to derive any clinical benefit from nivolumab single agent therapy as assessed by the investigator which would allow continuation of nivolumab monotherapy.
- The individual case must be discussed with the medical monitor prior to cross over.

Subjects crossing over to Arm N-I will start treatment at Day 1 Week 1 as described for subjects originally assigned to Arm N-I. Subjects who cross over and subsequently have an objective response in Arm N-I will not be considered in the decision making for Arm N-I proceeding to Stage 2.

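### Crossover-period safety is summarised by tumor type without the N-I dose level received, so regimens are mixed wherever subjects crossed over to more than one level

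*SAP*

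**What the plan says.** All references are to SAP version 2.0 unless stated.

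- **Crossover regimen (section 2.1, crossover paragraph).** One condition for crossover is that "at least 6 subjects have been exposed to the dose level used for Stage 1 of the N-I regimen". The same bullet adds: "In case Dose Level 2b has been activated and completed the safety assessment, subjects for cross over will be assigned to Dose Level 2b". Subjects then start as if newly assigned to Arm N-I.
- **The two levels (section 2.1).** Dose Level 2 is "Nivolumab (1 mg/kg) + Ipilimumab (3 mg/kg) Q3W for 4 doses" and Dose Level 2b is "Nivolumab (3 mg/kg) + Ipilimumab (1 mg/kg) Q3W for 4 doses". Both are followed by nivolumab 3 mg/kg Q2W.
- **Safety (section 7.6).** All treated subjects are summarised by cohort. Two further groups follow: "all dose escalation subjects, by tumor type; and all crossover subjects, by tumor type".
- **Exposure (section 7.4.3).** Summaries are "based on exposure data collected in treated crossover subjects on or after the first date of active ipilimumab therapy". No grouping is named.
- **Response (section 7.5.1.1).** "For the analysis of crossover subjects during crossover period, ORR will also be summarized". Again no grouping is named.
- **Default (section 7.1).** Where nothing else is said, tables are by cohort with a total.
- **Populations (sections 6.2 and 6.3).** The as-treated group follows the IVRS assignment, unless the wrong drug was given throughout. Crossover subjects form one undivided set.

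**The concern.** Nivolumab-ipilimumab toxicity is of interest by regimen, and the plan has several regimens because it treats dose level as something that may matter. For crossover subjects, section 7.6 names tumor type and leaves dose level out, in the same sentence that uses cohort for all treated subjects. Followed as written, it puts subjects given different ipilimumab and nivolumab doses in one column. The split between them is set by when Dose Level 2b opened in that tumor type relative to each subject's progression.

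This column is also the main tabulated home of these events. Section 7.6 cuts adverse events at the first crossover dose when the original treatment is analysed, so the by-cohort tables do not show them. If the crossover table cannot attribute toxicity to a regimen, no other summary in the plan clearly does.

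**Working it through.** The plan states no figure on this point, so there is none to reproduce. The check sets the sections side by side and adds one small calculation.

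**Step 1. Can two regimens occur in one crossover group?** Section 2.1 does not spell out the level used before Dose Level 2b is available. The natural reading is the Stage 1 level of Arm N-I, because the exposure condition refers to it. After Dose Level 2b is active and assessed, crossover goes to 2b. Within one tumor type, early and late crossovers can therefore receive different levels.

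**Step 2. Does any rule restore the dose level?**

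| Section | Grouping of crossover-period results |
|---|---|
| 7.6 safety | tumor type |
| 7.4.3 exposure | none stated |
| 7.5.1.1 ORR | none stated |
| 7.1 default | cohort, not defined for crossover subjects |
| 6.2 as treated | IVRS-assigned arm; no post-crossover rule |
| 6.3 crossover population | one set |

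None of these separates crossover subjects by the N-I level received.

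**Step 3. How far apart are the regimens?** Nominal combination-phase total = dose per infusion × 4.

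| | Nivolumab (mg/kg) | Ipilimumab (mg/kg) |
|---|---|---|
| Dose Level 2 | 4 × 1 = 4 | 4 × 3 = 12 |
| Dose Level 2b | 4 × 3 = 12 | 4 × 1 = 4 |

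Each drug differs by 12/4 = 3-fold, in opposite directions. This applies where Stage 1 used Dose Level 2.

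**Step 4. What does a pooled figure show?** Let w be the share of a tumor type's crossover subjects on Dose Level 2, and assume all four doses are given. Pooled mean ipilimumab = 12w + 4(1 − w) = 4 + 8w mg/kg. The SAP does not give w, so the range is 4 (w = 0) to 12 (w = 1). At an assumed w = 0.5 it is 4 + 8 × 0.5 = 8 mg/kg, which neither regimen delivers. A pooled adverse event rate or ORR is weighted by w in the same way. The documents give no crossover-period rates by level, so no size can be put on that distortion.

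**Step 5. Which summaries are affected?** Cumulative dose, adverse event rates and ORR are. Relative dose intensity is affected less, because Table 7.4.1-1 scales it to the subject's nominal dose.

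**The case against.** The strongest reply is that little rests on these tables, and much of it stands.

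- **The by-arm results are protected.** Adverse events and ORR in the original period are truncated at crossover (sections 7.6 and 7.5.1.1). Responses after crossover do not count towards the Arm N-I Stage 2 decision (section 2.1). No test or decision uses the crossover summaries. A reader might infer that the primary or secondary by-arm estimates are contaminated; the documents show they are not.
- **Mixing is possible but not shown.** A reader might infer that the crossover results correspond to no regimen at all. That goes too far. A tumor type whose crossovers all received one level still describes that level, and the SAP gives no counts. Ovarian cancer has no Arm N. The later SCLC expansion SAP records that crossover was confined to the original cohorts, with two exceptions in the SCLC expansion.
- **Exposure and ORR are not stated to be pooled by tumor type.** That grouping is written for safety alone. For the other two the defect is an unstated grouping and an undefined default.
- **Dose escalation is not the same case.** The quoted sentence also groups escalation subjects by tumor type, and a reader might infer that tolerability by level is lost there too. The documents do not support this. Escalation subjects also fall within all treated subjects by cohort, section 2.1 uses the word cohort at dose level, and section 7.5.4 provides for data review to determine the maximum tolerated level.
- **Other material may help.** By-subject exposure listings are planned (section 7.4.1), and swimmer plots mark crossover (section 7.5.1.1). The Core Safety SAP and the Data Presentation Plan are not shown and could add dose-level columns. Listings do not replace a summary by regimen, though, and section 7.6 itself fixes the grouping for this study.

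**Conclusion.** The point holds in a limited form. Section 7.6 fixes a grouping for crossover safety that omits the N-I dose level, while section 2.1 lets that level change over time. In any tumor type where subjects crossed over to both levels, the crossover-period adverse event rates cannot be attributed to either regimen. For post-crossover exposure and ORR, the plan leaves the grouping open and does not say what cohort means.

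The contrast can be as large as 12 against 4 mg/kg of nominal ipilimumab, and the reverse for nivolumab. This rests on three assumptions: that Stage 1 used Dose Level 2 in the tumor type concerned, that subjects crossed over both before and after Dose Level 2b became available, and that all four doses were given. The consequence is confined to descriptive, supplementary summaries. It is a cheap improvement in reporting, not a threat to the trial's main conclusions.

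**What to change.** 1. In section 7.6, summarise crossover-period safety by tumor type and by the N-I dose level received at crossover, with the pooled tumor-type column as a supplement.
2. In sections 7.4.3 and 7.5.1.1, state the same grouping for post-crossover cumulative dose and ORR.
3. In section 6.2 or 6.3, define cohort for crossover subjects as tumor type combined with N-I dose level received after crossover, so that the section 7.1 default has a meaning for them.

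The cost is a few lines of SAP text and additional table columns. The dose data needed are already collected: Table 7.4.1-1 and its notes draw on infusion volumes and weight from the CRF and nominal nivolumab dose from IVRS. The downside is small cells in some tumor types, which is why the pooled column should stay. No dose, crossover condition or other clinical rule changes.
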